1. INTRODUCTION

This Part 1 Statistical Analysis Plan (Part 1- SAP) specifies definitions of analysis sets, key derived variables, and statistical methods for analysis of safety and efficacy for the Dose Escalation (Part 1) part of the Phase 2 study. This SAP is based on the Clinical Protocol JNJ-64179375THR2001 amendment dated September 11, 2017. Titles, mock-ups and programming instructions for all statistical outputs (tables, figures, and listings) will be provided in a separate document entitled Data Presentation Specifications (DPS). A separate Part 2 SAP will address the analyses pertaining to Part 2 of the study.

Part 1- SAP and its associated DPS will be used to generate a Topline report at the end of Part 1 of the study.

1.1. Trial Objectives

Part 1

In men and women undergoing primary unilateral total knee replacement (TKR) surgery, after single-ascending intravenous (IV) doses of JNJ-64179375 or 10 to 14 days of oral apixaban:

Primary Objective

The primary objective is to assess the safety and tolerability of JNJ-64179375 for each dose level with a focus on evaluating major bleeding events for dose escalation within Part 1 and any bleeding events (the composite of major, clinically relevant nonmajor, and minimal bleeding events) for the selection of doses for Part 2.

Secondary Objectives

- To assess the dose response of JNJ-64179375 for the occurrence of the composite endpoint of any bleeding events, the composite endpoint of major or clinically relevant nonmajor bleeding events, and the individual components of the any bleeding event endpoint
- To assess the dose response of JNJ-64179375 for the prevention of total venous thromboembolism (VTE) (proximal and/or distal DVT [asymptomatic confirmed by venography assessment of the operated leg or objectively confirmed symptomatic], nonfatal PE, or any death) and the individual components of total VTE

Other Secondary Objectives

- To assess the effect of individual doses of JNJ-64179375 compared with apixaban for both efficacy and safety endpoints, with the goal to identify a studied or model-predicted dose with the most promising benefit-risk profile for a more extensive evaluation in Phase 3
- To assess the effect of JNJ-64179375 compared with apixaban on wound or joint complications in the operated leg

Exploratory Objectives

- To assess the PK, PD, and PK/PD relationships of JNJ-64179375 in men and women undergoing primary unilateral TKR surgery and the relation of these measures to efficacy and safety endpoints (eg, exposure-response analyses)

[figure not shown]
1.2. Trial Design

This is a randomized, double-blind, double-dummy, active-controlled, multicenter, dose-escalation and dose-finding study of JNJ-64179375. The study has 2 parts, dose-escalation and dose-response confirmation, and will be conducted in subjects undergoing primary unilateral elective TKR surgery. Part 1 will assess the safety of single-ascending IV doses of JNJ-64179375 while Part 2 will confirm the safety of the doses selected from Part 1 and will assess the efficacy dose response with respect to the selected doses in the parallel groups. Subjects will participate in either Part 1 or Part 2 only.

For each subject in each part, the study will be conducted in 3 phases: an up to 30-day screening phase before surgery, a 14-day double-blind dosing phase, and a 16-week follow-up phase. The total duration of the subject's participation in Part 1 or Part 2 after randomization will be approximately 18 weeks.

Following primary unilateral elective TKR surgery, eligible subjects in Part 1 will be randomly assigned to a single-ascending IV dose of JNJ-64179375 or apixaban 2.5 mg given orally twice daily for 10 to 14 days. Six cohorts of up to approximately 50 unique subjects per cohort (total of up to approximately 300 unique subjects) are planned but the number of cohorts and the size of each cohort may be adjusted based on the ongoing unblinded data review by the Operations Committee (OC). Within each cohort, subjects will be randomized in a 4:1 ratio to JNJ-64179375 or apixaban, respectively (ie, approximately 40 subjects to JNJ-64179375: approximately 10 subjects to apixaban). JNJ-64179375 will be administered in a dose-escalation manner, with planned doses of 0.3, 0.6, and 1.2 mg/kg in Cohorts 1, 2, and 3, respectively. In Part 1, the OC will be responsible for reviewing ongoing safety and efficacy data by unblinded subject treatment assignments approximately every 1 to 3 weeks. Subjects enrolled in the optional cohorts will receive doses of JNJ-64179375 in the range of 0.1 to 1.8 mg/kg, which will be dependent on the available preliminary safety, tolerability, efficacy, PK, and PD data obtained from the preceding cohorts (refer to Section 6, Dosage and Administration for additional details). After all the subjects in Part 1 are expected to have completed the Day10-14 visit, an unblinded data review will be conducted by the OC, Steering Committee (SC), Independent Data Monitoring Committee (IDMC), and sponsor to determine the dose range and doses for Part 2. A schematic diagram of the study design (Part 1) is provided in [Figure 1](#) below.

Figure 1: Schematic Overview of Part 1 of the Study

‡ Double-dummy design: Subjects in both parts will receive a single dose of IV JNJ-64179375 or JNJ-64179375 placebo and 10 to 14 days of apixaban or apixaban placebo PO BID, followed by unilateral venography and follow-up study visits through Week 18. Unique subjects will be enrolled in each part and within each part unique subjects will be enrolled in each cohort.

† Six cohorts of up to approximately 50 unique subjects per cohort (total of up to approximately 300 unique subjects) are planned but the number of cohorts and the size of each cohort may be adjusted based on the ongoing unblinded data review by the Operations Committee.

BID = twice daily; IV = intravenous; PO = by mouth

1.3. Statistical Hypotheses for Trial Objectives

The primary objective of the study in Part 1 is to assess the safety and tolerability of a range of doses of JNJ-64179375 with respect to major bleeding events for dose escalation and any bleeding events (the composite of major, clinically relevant nonmajor, and minimal bleeding events) for the selection of doses for Part 2 and hence, no statistical hypothesis will be tested. Eighty percent confidence intervals for the odd ratio of each dose over apixaban event rate with respect to major bleeding and any bleeding events (the composite of major, clinically relevant nonmajor [CRNM], and minimal bleeding events) will be constructed. For the secondary objectives, dose response of JNJ-64179375 will be assessed with respect to any bleeding events, the composite endpoint of major or clinically relevant nonmajor bleeding events, and the individual components of the any bleeding events, total VTE and individual components of total VTE events.

[figure not shown]
1.4. Sample Size Justification

A total of 1,500 subjects are planned for this study, of which up to 300 subjects will be enrolled in Part 1 and the remainder for the entire study will be enrolled in Part 2. In Part 1, the sample size is not based on hypothesis testing but rather on making a preliminary assessment of the bleeding risk for the doses of JNJ-64179375. The event rate of any bleeding up to 14 days for

apixaban 2.5 mg twice daily is expected to be between 5% and 10%. Figure 2 shows the probability to flag a higher event rate compared to apixaban for any dose of JNJ-64179375 in Part 1, assuming that the true underlying bleeding event rate in the apixaban group is 5%, 7.5%, or 10%. The figure presents the numbers of subjects in the JNJ-64179375 and apixaban treatment groups in rows and columns, respectively. The assumed event rate in the JNJ-64179375 group is presented as the relative risk to apixaban in the horizontal axis; the statistical comparison is based on the difference between event rates.

When the true underlying event rate in the apixaban group is 7.5%, there is a 67% probability for a dose of JNJ-64179375 to have the lower bound of the 1-sided 90% CI exclude 0 if the true relative risk (or risk ratio) is 3 (ie, the true underlying event rate in the JNJ-64179375 group is 22.5%), with 40 subjects in the JNJ-64179375 group (ie, any 1 planned cohort of JNJ-64179375 subjects) and 30 subjects in the apixaban group (ie, pooled apixaban subjects from 3 planned cohorts). The probability will increase to 81% when the dose of JNJ-64179375 is repeated in another planned or optional cohort, where there will be 80 subjects in the JNJ-64179375 treatment group and 40 subjects in the pooled apixaban group.

Figure 2: Probability to Flag a Higher Event Rate in the JNJ-64179375 Group Than in the Apixaban Group at a 1-Sided, 10% α -Level

1.5. Randomization and Blinding

Central randomization will be implemented in this study. In Part 1, within each of the planned cohorts, subjects will be randomized in a 4:1 ratio to JNJ-64179375 or apixaban, respectively (ie, approximately 40 subjects to JNJ-64179375: approximately 10 subjects to apixaban) based on a computer-generated randomization schedule prepared by or under the supervision of the sponsor. The randomization will be balanced by using randomly permuted blocks with no stratification in Part 1. The interactive web response system (IWRS) will assign a unique treatment code, which will dictate the treatment assignment for the subject. The requestor must use his or her own user

identification and personal identification number when contacting the IWRS, and will then give the relevant subject details to uniquely identify the subject. Separate randomization schedules will be used for Part 1 and Part 2 of the study.

The investigator will not be provided with randomization codes. The codes will be maintained within the IWRS, which has the functionality to allow the investigator to break the blind for an individual subject. Data that may potentially unblind the treatment assignment (ie, coagulation testing, study drug concentrations, antibodies to JNJ-64179375, study drug preparation/accountability data, treatment allocation, and biomarker laboratory data) will be handled with special care to ensure that the integrity of the blind is maintained and the potential for bias is minimized. This can include making special provisions, such as segregating the data in question from view by the investigators, clinical team, or others as appropriate until the time of database lock and unblinding. To maintain the blind of the study, the investigator should not measure coagulation assays locally unless considered necessary for subject clinical care. In addition, the investigator will not receive the results of the PD parameters from the central specialty laboratory during the conduct of the study.

In general, randomization codes will be disclosed fully only if the study is completed and the clinical database is closed at the end of the entire study. However, the randomization codes and the translation of randomization codes into treatment and control groups will be disclosed to those authorized individuals of the OC for the ongoing data reviews in Part 1.

Using the randomization code, an unblinded pharmacist or other appropriately licensed and authorized health professional at each study site will prepare an individual study drug dose of JNJ-64179375 in a 50-mL normal saline IV bag as per the directions in the Investigational Product Preparation Instructions (IPPI). Subjects randomized to apixaban will receive a 0.9% normal saline IV bag with no active study drug. All study drugs will have a blinded label applied prior to dispensing.

Using the randomization code, the pharmacist or other appropriately licensed and authorized health professional will dispense a bottle of blinded oral study drug (over-encapsulated apixaban tablets or matching apixaban placebo capsules) to each subject at the time of randomization. The subject will be administered the capsules from the bottle while hospitalized and will be given the bottle for outpatient use at the time of discharge from the hospital.

2. GENERAL ANALYSIS DEFINITIONS

2.1. Visit Windows

As subjects do not always adhere to the protocol visit schedule, the following rules are applied to assign actual visits to analysis visits. Listed below are the visit windows and the target days for each visit. The reference day is Study Day 1 (see section 2.6 for definition). If a subject has 2 or more actual visits in one visit window, the visit closest to the target day will be used as the protocol visit for that visit window. The other additional visit(s) will not be used in the summaries or analyses but they can be used for determination of clinically important endpoints. If 2 actual visits are equidistant from the target day within a visit window, the later visit is used.

All assignments will be made in chronological order. Once a visit date is assigned to a visit window, it will no longer be used for a later time point except for the endpoint. Listed below (Table 1) are the visit windows and the target days for each visit defined in the protocol.

Table 1: Visit Windows

Parameter	Study Phase	Scheduled Visit Number	Time Interval (label on output)	Time Interval (Day)*	Target Time Point (Day)
Vital signs	Screening	1	Screening	< 1	-30 to -1
	DB-Dosing	2	Baseline	<=1	1
		3	Day 2	<=2	2
		4	Day 3	<=3	3
		5	Day 7	4 to 9	7
		6	Day 10-14 (EOD/EW)	10 to 27	The midpoint in the 10 to 14-day window
Follow-up	7	FU Week 5	28 to 55	35	
	8	FU Week 10	56 to 111	70	
	9	FU Week 18	112 to 140	126	
Clinical Laboratory Assessments	DB-Dosing	2	Baseline	<=1	1
		3	Day 2	<=9	2
		6	Day 10-14 (EOD/EW)	10 to 27	The midpoint in the 10 to 14-day window
	Follow-up	7	FU Week 5	28 to 55	35
		9	FU Week 18	112 to 140	126
Venography of the operated leg	DB-Dosing	6	Day 10-14 (EOD/EW)	any day	10 to 14
Symptomatic thrombotic events	DB-Dosing	2	Baseline	<=1	1
		3	Day 2	<=2	2
		4	Day 3	<=3	3
		5	Day 7	4 to 9	7
		6	Day 10-14 (EOD/EW)	10 to 27	10 to 14
		Follow-up	7	FU Week 5	28 to 55
	8		FU Week 10	56 to 111	70
	9		FU Week 18	112 to 140	126

*Relative to Study Day 1; DB = Double-Blind; EOD = End of dosing; EW = Early withdrawal

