Approximate Total^c for Sparse PK subjects 80.4 ADA=antidrug antibody; aPTT=activated partial thromboplastin time; ECT=ecarin clotting time; No.=number; PD = pharmacodynamics; PK=pharmacokinetic, PT = prothrombin time; TT = thrombin time

Some sample volumes will vary slightly for subjects in Japan (due to customs requirements for laboratory tubes).

h Calculated as number of samples per subject multiplied by volume of blood per sample.

с Repeat or unscheduled samples may be taken for safety reasons or technical issues with the samples.

Note: An indwelling IV cannula may be used for blood sample collection.

Additional blood samples may be collected, if necessary, for additional safety, PK, or PD assessments based on emerging data, but the total blood volume collected from an individual subject during this study will not exceed 200 mL without prior Independent Ethics Committee (IEC) or Institutional Review Board (IRB) and health authority approvals. Repeat or unscheduled samples may be taken for safety reasons or for technical issues with the samples and do not require prior IEC/IRB and health authority approvals.

Health resource utilization data will be collected. Refer to Section 9.6, Health Resource Utilization for details.

9.1.2. **Screening Phase**

The screening phase will occur up to 30 days before randomization, pre- or postoperatively. Potential subjects may be evaluated for eligibility before or after their unilateral elective TKR surgery. Final eligibility must be confirmed after surgery, prior to randomization.

Prior to conducting any study-related procedure, the investigator (or designated study personnel) will review and explain the written ICF to each subject. No study procedures can be performed until the subject signs the ICF. At the time of informed consent, 2 alternative means of contact for the each subject will be collected (eg, contact information of the subject's children, spouse, significant other, caretaker, legal representative, or health care professional). Details regarding the TKR surgery and the post-surgery management (eg, type of anesthesia, procedure duration, cement use, tourniquet use and duration, drain use and volume, and use of all mechanical VTE prophylaxis methods) will be collected in the eCRF. In addition, the subject will respond to questions (see Attachment 1) regarding his or her family and personal bleeding history, including any bleeding from previous surgical procedures.

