2.7. Baseline and Endpoint

Baseline is defined as the last observation prior to the start of the first study agent administration or randomization date.

Endpoint is defined as the last available postbaseline result within the analysis period. Unscheduled visit results are included in this definition and will be considered as the endpoint value if the unscheduled visit result is the last postbaseline result available within the analysis period. The result refers to an event.

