6.5. Clinical Laboratory Tests

All clinical laboratory tests will be displayed for the subjects included in the safety analysis set by visit and treatment group.

Laboratory assessments (hematology, chemistry and urinalyses) were made at Day 0, Day 2, Day 10-14, Week 5 and Week 18 Visits.

Descriptive statistics will be presented for all chemistry, hematology, and urinalysis laboratory tests at scheduled time points.

Change from baseline to scheduled time point will be summarized for chemistry, hematology, and urinalysis tests and displayed by visit and treatment group.

Number and percentage of subjects with postbaseline clinically important laboratory values and/or markedly abnormal postbaseline values will be presented by visit and treatment group.

The clinically important laboratory findings to be reported are described below:

- AST (U/L): 3x ULN
- ALT (U/L): 3x ULN

Markedly abnormal laboratory findings to be reported are described below:

- AST (U/L): 5x ULN
- ALT (U/L): 5x ULN
- Hgb < 80 g/L
- Plt < 50 K
- Cr > 176.8 $\mu\text{mol/L}$

A listing of clinically important and markedly abnormal laboratory values will be provided.

Shift tables will be provided summarizing, by treatment group, the shift in laboratory values from baseline to each scheduled time point with respect to abnormality criteria (low, normal, high).

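### Markedly abnormal laboratory values are counted only by visit, one value per window, so extra values and any value on Days 56-111 normally drop out of the count

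*SAP*

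**What the plan says.** **How a value is chosen (SAP 2.1).** "If a subject has 2 or more actual visits in one visit window, the visit closest to the target day will be used". Ties are settled as follows: "If 2 actual visits are equidistant from the target day within a visit window, the later visit is used". Remaining visits are handled thus: "The other additional visit(s) will not be used in the summaries or analyses but they can be used for determination of clinically important endpoints". The SAP does not define which endpoints that exception covers.

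**Laboratory windows (SAP Table 1).** The postbaseline rows are Day 2 (to Day 9), Day 10-14 (Days 10-27), Week 5 (Days 28-55) and Week 18 (Days 112-140). There is no Week 10 laboratory row. Vital signs and symptomatic thrombotic events do have one, for Days 56-111.

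**How abnormal values are counted (SAP 6.5).** "Number and percentage of subjects with postbaseline clinically important laboratory values and/or markedly abnormal postbaseline values will be presented by visit and treatment group". AST and ALT at 3 times the upper limit are called clinically important. Hemoglobin below 80 g/L, platelets below 50 K, high creatinine, and AST and ALT at 5 times the upper limit are called markedly abnormal. No count over the whole period, and no worst-value count, is stated. A listing is planned: "A listing of clinically important and markedly abnormal laboratory values will be provided".

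**When samples are taken.** SAP 6.5: "Laboratory assessments (hematology, chemistry and urinalyses) were made at Day 0, Day 2, Day 10-14, Week 5 and Week 18 Visits". Protocol 9.1.1 allows more: "Repeat or unscheduled samples may be taken for safety reasons or for technical issues with the samples".

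**The concern.** Bleeding is the main expected harm, and the primary objective of Part 1 is safety and tolerability at each dose. No hematology is scheduled between Day 2 and the Day 10-14 visit, or between Week 5 and Week 18. A value in those intervals is therefore likely to be a repeat or unscheduled sample, possibly taken because something was wrong. If such a value is markedly abnormal, the stated rules normally keep the routine value in the table and leave the abnormal one out. The table could then show fewer subjects with a markedly abnormal value in a dose group than the database holds.

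**Working it through.** The plan gives no figure to reproduce. The check applies the SAP 2.1 rules to every possible day.

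**Inputs.** The windows and targets come from SAP Table 1. The Day 10-14 target is the midpoint of that range, Day 12. Postbaseline windows are taken to start at Day 2, and scheduled samples are first assumed to fall on target: Days 2, 12, 35 and 126.

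**Rule.** Within a window, keep the value with the smallest |day − target|; on a tie, keep the later one. One extra value is added on each day in turn to see whether it enters a by-visit count.

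| Days of the extra value | Window and target | Enters the count? | Days lost |
|---|---|---|---|
| 3-9 | Day 2, target 2 | No: distance 1 to 7 against 0 | 7 |
| 10-11 and 13-27 | Day 10-14, target 12 | No | 2 + 15 = 17 |
| 28-34 and 36-55 | Week 5, target 35 | No | 7 + 20 = 27 |
| 56-111 | none | No: nothing to be assigned to | 111 − 56 + 1 = 56 |
| 112-125 and 127-140 | Week 18, target 126 | No | 14 + 14 = 28 |

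The total is 7 + 17 + 27 + 56 + 28 = 135, which is all 139 days from Day 2 to Day 140 except the four scheduled ones. Of these, 79 are lost through the nearest-to-target rule and 56 through the missing window.

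**When samples are not on target.**
- Day 2 sample missing: a value on Days 3-9 becomes the Day 2 value and is counted. The lost days fall to 135 − 7 = 128.
- Day 10-14 sample taken on Day 14 (distance 2): an extra value on Day 11, 12 or 13 (distance 1, 0, 1) replaces it and is counted. An extra value on Day 10 ties, and the later Day 14 value is kept.
- Days 56-111: no timing of the scheduled samples brings such a value into a visit count.

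**Invented illustration.** Hemoglobin is 98 g/L on Day 2 and 76 g/L on Day 6. The distances are 0 and 4, so 98 is kept. Since 98 is not below 80, the subject shows no markedly abnormal value at the Day 2 visit.

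**Do other clauses recover the value?**
- The SAP 2.1 exception is permissive and undefined. SAP 6.5 applies the term clinically important to the AST and ALT findings and puts hemoglobin under the other label. Exclusion is the more natural reading but is not certain. The exception also concerns extra visits within a window, so it does not clearly reach Days 56-111.
- SAP 2.7 says of its endpoint value: "Unscheduled visit results are included in this definition and will be considered as the endpoint value". That value is the last postbaseline result, not the worst.
- The listing may show the value but gives no number or percentage by treatment group.
- By contrast, SAP 6.6 words its summary of vital-sign abnormalities as an incidence among subjects with a postbaseline assessment, not by visit.

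**The case against.** The strongest reply is that this table is not how the trial measures bleeding.

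- Hemoglobin associated with a bleed is recorded with the bleeding event and adjudicated (Protocol 9.7.2.1.1 and 11.11.4). Major bleeding rests on items such as a hemoglobin fall of 20 g/L or transfusion (Protocol Attachment 2), not on the 80 g/L threshold.
- None of the suggested stopping criteria in SAP 3.1.1 uses a laboratory count.
- Clinically relevant laboratory changes are also recorded as adverse events (Protocol 9.7.3). SAP 6.4 counts these by treatment group from first dose to last contact.

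All of this stands. A reader might infer that bleeding is under-counted, or that differences between doses shrink. The documents do not support either inference.

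The missing Week 10 window also follows from the visit schedule. The 56 days are 40% of 140 calendar days (56/140), and a reader might take that as the share of data lost. It is only calendar time with no planned hematology. The Time and Events Schedule marks no hematology at unscheduled visits, extra samples are permitted rather than required, and a hemoglobin drawn at an acute bleed may be a local result held on the bleeding form. Few such values may be in the laboratory data.

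Finally, Protocol 11.9 plans frequency tabulations of abnormalities without a by-visit limit, and the separate Data Presentation Specifications, not available here, may already contain an overall row. That is possible, but the SAP as written does not ask for one.

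**Conclusion.** The point holds for the laboratory abnormality table only. Under the stated rules, an extra or unscheduled value is normally left out of the by-visit count when a value nearer the target exists, in any window. A value on Days 56-111 is always left out, because no laboratory window covers those days. The two causes are separate: the nearest-to-target sentence does not create the Days 56-111 gap.

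It would be too strong to say that every Day 3-9 value is lost, since one is counted when no value lies nearer Day 2. It would also be too strong to say that the treatment-group safety results as a whole miss these events.

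The number of subjects affected cannot be derived from the documents. The conclusion assumes that the SAP 2.1 exception does not cover the SAP 6.5 criteria and that the table specifications add no overall row. This is a worthwhile, inexpensive improvement rather than a flaw in the primary safety analysis.

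**What to change.** In SAP 6.5, add for each analysis period and treatment group the number and percentage of subjects with any postbaseline value in the study database that meets each clinically important or markedly abnormal criterion. Include scheduled and unscheduled values, in or out of a visit window. The three observation periods that SAP 2.4.4 sets for bleeding could serve. Exempt this count from the visit-selection rule of SAP 2.1.

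In SAP 2.1, state whether the exception for clinically important endpoints includes the SAP 6.5 laboratory criteria.

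Keep the by-visit tables unchanged. Add a footnote to the new count that subjects sampled more often have more chances to qualify.

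The cost is a few sentences in the SAP and one extra row per criterion and period. No new data are collected. The row can recover only values that reach the study database; a local hemoglobin held only on the bleeding form counts only if it is entered there as a usable result.
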